6 ASSESSMENT OF SAFETY

During recruitment it is explained to the participant that this is a research study. They are also told the types of questions that will be asked and that they have the right to decline participation or withdrawal at any time. Participants are also explained the potential risk of distress due to the sensitive nature of the questions. The participant is explained their rights and what the study is clearly.

6.1 Specification of Safety Parameters

6.1.1 *Unanticipated Problems*

The Office for Human Research Protections (OHRP) considers unanticipated problems involving risks to subjects or others to include, in general, any incident, experience, or outcome that meets **all** of the following criteria:

- unexpected in terms of nature, severity, or frequency given (a) the research procedures that are described in the protocol-related documents, such as the IRB-approved research protocol and informed consent document; and (b) the characteristics of the subject population being studied;
- related or possibly related to participation in the research (“possibly related” means there is a reasonable possibility that the incident, experience, or outcome may have been caused by the procedures involved in the research); and
- suggests that the research places subjects or others at a greater risk of harm (including physical, psychological, economic, or social harm) than was previously known or recognized.

6.1.2 *Adverse Events*

An adverse event is any untoward or unfavorable medical occurrence in a human subject, including any abnormal sign (for example, abnormal physical exam or laboratory finding), symptom, or disease, temporally associated with the subject’s participation in the research, whether or not considered related to the subject’s participation in the research.

6.1.3 *Serious Adverse Events*

A serious adverse event (SAE) is one that meets one or more of the following criteria:

- Results in death
- Is life-threatening (places the subject at immediate risk of death from the event as it occurred)
- Results in inpatient hospitalization or prolongation of existing hospitalization

- Results in a persistent or significant disability or incapacity

6.2 Characteristics of an Adverse Event

6.2.1 Relationship to Study Intervention

To assess relationship of an event to study intervention, the following guidelines are used:

1. Related (Possible, Probable, Definite)
 - a. The event is known to occur with the study intervention.
 - b. There is a temporal relationship between the intervention and event onset.
 - c. The event abates when the intervention is discontinued.
2. Not Related (Unlikely, Not Related)
 - a. There is no temporal relationship between the intervention and event onset.
 - b. An alternate etiology has been established.

6.2.2 Expectedness of SAEs

The Study PI will be responsible for determining whether an SAE is expected or unexpected. An adverse event will be considered unexpected if the nature, severity, or frequency of the event is not consistent with the risk information previously described for the intervention.

6.2.3 Severity of Event

The following scale will be used to grade adverse events:

1. Mild: no intervention required; no impact on activities of daily living (ADL)
2. Moderate: minimal, local, or non-invasive intervention indicated; moderate impact on ADL
3. Severe: significant symptoms requiring invasive intervention; subject seeks medical attention, needs major assistance with ADL

6.3 Reporting Procedures

6.3.1 Unanticipated Problem Reporting to IRB and NIAAA

Incidents or events that meet the OHRP criteria for unanticipated problems require the creation and completion of an unanticipated problem report form. OHRP recommends that investigators include the following information when reporting an adverse event, or any other incident, experience, or outcome as an unanticipated problem to the IRB:

- appropriate identifying information for the research protocol, such as the title, investigator's name, and the IRB project number;
- a detailed description of the adverse event, incident, experience, or outcome;
- an explanation of the basis for determining that the adverse event, incident, experience, or outcome represents an unanticipated problem;
- a description of any changes to the protocol or other corrective actions that have been taken or are proposed in response to the unanticipated problem.

To satisfy the requirement for prompt reporting, unanticipated problems will be reported using the following timeline:

- Unanticipated problems that are serious adverse events will be reported to the IRB and to NIAAA within 1 week of the investigator becoming aware of the event.
- Any other unanticipated problem will be reported to the IRB and to NIAAA within 2 weeks of the investigator becoming aware of the problem.
- All unanticipated problems should be reported to appropriate institutional officials (as required by an institution's written reporting procedures), the supporting agency head (or designee), and OHRP within one month of the IRB's receipt of the report of the problem from the investigator.

6.3.2 Serious Adverse Event Reporting to NIAAA

Procedures and timeline for reporting AEs to NIAAA.

AEs will be reported to the NIAAA PO at least once per year as a part of the annual progress report. These reports will describe the event, when it occurred, the study arm of the participant, and the outcome/resolution. If there are no AEs in a given year, the report will include a statement to this effect.

Procedures and timeline for reporting SAEs to NIAAA.

SAEs, whether or not anticipated, will be reported to the NIAAA PO within 24 hours of the event by email. This 24 hour notification will include a brief explanation of the SAE

[figure not shown]
and when it occurred. A written follow up will be sent within 72 hours of the event. This written follow up will include information on the date of the event, what occurred, actions taken by project staff, planned follow up (if any), the intervention group/study arm of the affected participant, whether the event appears to be related to the intervention, and whether participant will continue in the study.

Reporting of IRB actions to NIAAA.

Follow-up reports to the NIAAA program official—made within 48 hours of IRB actions—will specify IRB actions related to study shut-down or changes. We will follow Wayne State University policy in the handling of all AEs and SAEs; see Appendix 1 for algorithm from the WSU IRB, which will be followed in all respects except with regard to unanticipated SAEs, which **will** be reported to NIAAA.

Wayne State University Risk-Adverse Event Algorithm:

Problems Involving Risk- Adverse Event Algorithm

7 STUDY OVERSIGHT

The Principal Investigator was responsible for monitoring the safety and efficacy of the interventions, executing the Data and Safety Monitoring Plan (DSM), and complying with all reporting requirements. The PI will provide a DSM report to NIAAA on an annual basis, as part of the progress report. The DSM report will include the participants' sociodemographic characteristics, expected versus actual recruitment rates, treatment retention rates, any quality assurance or regulatory issues that occurred during the past year, summary of adverse events (AEs) and serious adverse events (SAEs), and any actions or changes with respect to the protocol. The report will also include, when available, the results of any efficacy data analysis conducted.

a. Data Monitoring Plan. Data was collected by researcher entry (interviews) or by direct participant entry (self-report) using secure technology (CIAS and Qualtrics; both of which use strong encryption and other data safety protocols). The codes that link participant names with study ID# were secured by the PI in a locked cabinet. All data was kept in the PI's lab.

The primary outcome was mean drinks per day over the past 30 days (as measured at both 1 and 3-month follow ups). Secondary outcome measures included past month heavy drinking days, alcohol-related consequences, and intention to reduce alcohol use. Outcome data was analyzed using ANCOVAs, factorial ordinal regression, or binary logistic regression, depending on each outcome's distribution. The alpha level will be set at 5%.

Data quality was facilitated by direct participant entry of most data directly into sophisticated data collection software, and use of double-entry for all data not entered directly by participants. Data quality was monitored regularly by Co-Investigator [name] (at Wayne State), in concert with the PI and Co-Investigator.

b. Safety Monitoring Plan. For this study, we used the FDA definition of serious adverse events (SAEs). Any SAE, whether or not related to study intervention, will be reported to the IRB and NIAAA. The initial SAE report will be followed by submission of a completed SAE report to both institutions. In the event that a participant either withdraws from the study or the investigator decides to discontinue a participant due to a SAE, the participant will be monitored by the investigator via ongoing status assessment until (1) a resolution is reached (i.e., the problem requiring hospitalization has resolved or stabilized with no further changes expected); (2) the SAE is determined to be clearly unrelated to the study intervention; or (3) the SAE results in death. Outcomes of SAEs will be periodically reported to NIAAA. A summary of the SAEs that occurred during the previous year will be included in the annual progress report to NIAAA.

8 STATISTICAL CONSIDERATIONS

8.1 Study Hypotheses

Factorial designs differ from randomized trials in several ways. Perhaps most importantly, in factorial designs each participant either receives or does not receive **each** independent variable. This allows analysis of each factor to utilize the entire sample, which in turn allows each main effect to be powered based on the entire sample rather than a fraction of the sample (as with randomized clinical trials). This efficiency makes factorial designs ideal for pre-trial optimization. Further, use of effect coding (-1, 1) rather than dummy coding (0, 1) renders orthogonal all main and interaction effects, increasing power for detection of interaction effects (Collins, 2009). Although R21 studies are not typically fully powered, the current N of 352, presuming use of intent to treat analysis, provides 80% power to detect main/interaction effects of $d \geq .3$.

Analyses will follow standard procedures for evaluating distributional assumptions, disproportionate or biased follow-up, and randomization success, and will utilize transformations and replacement of missing data using multiple imputation as appropriate. Primary analyses will evaluate main and interaction effects on mean drinks/day in the past 30 days, as measured by both the TLFB and the Quantity/Frequency Questionnaire. (Secondary analyses will similarly examine main and interaction effects on binge drinking days, drinking consequences, and pre-post changes in intention to reduce drinking.) A single 2X2X2X2X2 ANCOVA (*or factorial ordinal/binary logistic regression, depending outcome distribution*) will test the following hypotheses:

- **Hypothesis 1.** There will be significant main effects on mean drinks/day for the two factors consistent with Common Factors Theory (empathy and positive regard).
- **Hypothesis 2.** There will be significant main effects on mean drinks/day for the two factors consistent with the Media Equation Theory (voice and narrator).
- **Hypothesis 3.** *There will be significant main effects on mean drinks/day for motivational content.*
- **Hypothesis 4.** Mean drinks/day will be lower when one or more of the common factors (empathy, positive regard) is combined with a voice and/or a narrator.
- **Hypothesis 5.** *Mean drinks/day will be lower when motivational content is combined with one or more common factors and/or with voice/narrator.*

Following MOST guidelines (Collins et al, 2009), if intervention components (or combinations of components) are clearly effective, we will proceed to developing an optimized intervention. If intervention components show some effectiveness, we will conduct refining experiments to explore what form/dose of the components will maximize effects. If there are no significant main or interaction effects, we will conduct additional exploratory/developmental studies using new factors.

V. Research Strategy: Limitations and Design Considerations

Given its status as an R21 application, this research aims to be innovative and to seek evidence of preliminary effects in an important area of research. Additionally, we note the following design considerations.

1. **Should we use college student participants?** *CDBIs for undergraduates generally contain the same content as those administered to clinical and community samples (e.g., normed feedback, change plan, etc; Larimer et al, 2007). Moreover, effect sizes for CDBIs in college vs. non-college samples do not differ (Portnoy et al, 2008). This initial, exploratory study will allow us to recruit participants in high numbers and over a short time period. We will test for generalizability—which we expect to be present—in future studies.*
2. **Are we under-powered?** Our proposed sample (N=352) will give us marginally sufficient power (80% power to detect effects up to $d=.3$). However, R21 exploratory studies typically lack even marginally sufficient power; we see this as a large exploratory study rather than as an underpowered confirmatory study, with its size made possible by our intentional use of a readily available sample.

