- The proposed study **was the first to experimentally evaluate the role of common factors in computer-delivered interventions**. Findings from the field of Human-Computer interaction suggest that individuals (1) react to computers in a social manner, especially when they include a voice or other “human” characteristics; Nass & Moon, 2000), and (2) respond positively to relational behaviors (e.g., flattery, empathy) expressed by computers (Bickmore et al, 2005). The current study was the first to apply these findings in a therapeutic context, or to use them to inform brief intervention development.
- The current study made use of **unique technology**. The software used in this study was highly interactive and individualized, and relied heavily on realistic interactions with a three-dimensional, animated narrator that could mimic the more conversational nature of person-delivered brief interventions. This narrator could speak, move, point, provide empathic reflections, and display emotional responses such as pleasure, surprise, sadness, and thoughtfulness. The uniquely interactive, lifelike nature of this software provides an ideal platform for examining common factors in CDBIs.
- Following the Multiphase Optimization Strategy (e.g., Collins et al., 2011), the current study used a **factorial design** to test 16 combinations of 4 common factors (Collins, Dziak, & Li, 2009). Because each participant either received or did not receive each common factor, analyses of all factors utilized the entire sample and thus were fully powered with a relatively small N. This unique factorial design allowed us to test not only the main effects of the four factors under study (one of

which is consistent with Common Factors Theory, and two of which are consistent with Media Equation Theory), but also **whether these factors interacted to result in better outcomes**.

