1.3 Study Objectives/Outcome Measures

1.3.1 Primary

The primary outcome will be mean drinks per day over the past 30 days (as measured at both 1 and 3-month follow ups). Outcome data will be analyzed using ANCOVAs, factorial ordinal regression, or binary logistic regression, depending on each outcome's distribution. The alpha level will be set at 5%.

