3 STUDY DESIGN

The purpose of this study was to develop a maximally effective computer-delivered brief intervention (CDBI) for reducing heavy alcohol use. To accomplish this we created 16 different versions of a CDBI in which common factors, use of a voice, use of an animated narrator, and motivational content were systematically manipulated using a factorial design. Participants were 352 male and female undergraduate students at Wayne State University recruited either through the Psychology department ‘subject pool’ or through ads placed on the university’s website. Eligible students needed to meet NIAAA--defined binge or heavy drinking criteria. Heavy drinking criteria: More than 3 (women)/4 (men) drinks per day, or more than 7 (women)/14 (men) drinks per week. Binge drinking criteria: more than 4 (women)/5 (men) drinks in a 2 hr. period.

The study consisted of a baseline assessment (45 minutes, in lab), a 1-month follow-up assessment (10 minutes, online), and a 3-month follow-up assessment (30 minutes, online). During all three assessments, participants completed questionnaires assessing demographics, past-month alcohol use, alcohol-related consequences, heavy episodic drinking, and motivation to reduce drinking. During the baseline and the 3-month follow-up assessments, participants were given a Timeline Follow-Back Interview to assess past month alcohol use. Additionally, during the baseline assessment, participants completed a brief (15 minute), computer-delivered intervention aimed at reducing heavy drinking. This intervention has been used in multiple previous studies and is based on the principles of motivational interviewing. At the end of each session, participants were fully debriefed and compensated with either course credit or an Amazon gift card (\$20 gift card for the baseline session, \$30 gift card for the 1-month follow-up, \$40 gift card for the 3-month follow-up).

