and motivation to reduce alcohol use. Participants who completed the survey received either course credit or a \$30 Amazon gift card (participant's choice).

5. 3-Month Follow-Up Session: Three months post-intervention, participants were e-mailed a link to a secure (30 minute) online survey (using Qualtrix). They completed all 1-month follow-up measures, as well as a computerized TLFB interview assessing past-month drinking. At the end of the session, they were given either course credit or a \$40 Amazon gift card (participant's choice).

Measures

Past Month Alcohol Use was assessed with two measures: (1) The Timeline Follow-Back interview (Sobell & Sobell, 1966), a highly reliable interview that uses a calendar and multiple procedures to aid retrospective reporting of substance use (Fals-Stewart et al, 2000) and (2) the 3-item Quantity/Frequency questionnaire (U.S. Dept. of Health and Human Services, 1995), a survey which assesses the quantity, frequency, and maximum number of drinks consumed in the past month. Past Month Alcohol Consequences was assessed using the Brief Young Adult Alcohol Consequences Questionnaire (Read et al, 2006), a well-validated questionnaire designed to assess high and low level drinking consequences commonly experienced by young adults. Motivation to Reduce Drinking was assessed with the Readiness to Change Scale (Sobell, 1996), a 4-item scale that assesses motivation and intention to reduce drinking. Intervention Empathy and Positive Regard were assessed with the The Participant Satisfaction Questionnaire (PSQ), a measure created for this study. The PSQ assessed the degree to which participants perceived that the intervention was empathic and respectful.

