5.3 Follow-ups (1-month and 3-month)

This study was designed to maximize the follow-up rate and therefore both follow-ups were administered online. One month post-intervention, participants were e-mailed a link to a brief (10 minute), secure online survey (using Qualtrics) which assessed mean drinks per day in the past 30 days, past month alcohol consequences, and motivation to reduce alcohol use. Participants who completed the survey received either course credit or a \$30 gift card (participant's choice).

The 3-Month Follow-Up online survey (using Qualtrics) included all 1-month follow-up measures, as well as a computerized TLFB interview assessing past-month drinking. At the end of the session, Participants were given either course credit or a \$40 gift card (participant's choice).

The gift cards were sent to participants' email address after the project coordinator confirmed completion of the online survey. At the very end of the study, all participants were emailed a debriefing letter describing the study in more detail.

An Explanation of the College Alcohol Study

Thank you for participating in the College Alcohol Study. We really appreciate your time and effort. Since you've just completed your last session, we want to explain to you what our study is about.

As you know, drinking alcohol can be associated with both good things, like relaxation, and bad things, like health problems. As a result, many people have mixed feelings about whether they want to reduce their alcohol use.

A number of different programs have been developed to help people better understand the pros and cons of drinking and decide whether it's worth it to them to reduce their alcohol use. However, these programs can be very different from one another. Some programs are computerized (like the one you interacted with during your first visit), whereas others use an actual person. Programs can also differ in their content and presentation. Currently, it's not clear which types of programs are most effective in helping people decide whether or not they want to change their drinking patterns.

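### The planned primary model has five two-level factors and treats empathy and positive regard as separate, but the trial manipulates four with those two combined; the primary outcome also has no lead variable and pairs an instrument with a visit at which it is not collected

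*Combined protocol and SAP*

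**What the plan says.** **Outcome.** Section 1.3.1 defines the primary outcome as "mean drinks per day over the past 30 days (as measured at both 1 and 3-month follow ups"); the Protocol Summary and Section 7 agree. Section 8.1 says main and interaction effects will be evaluated "on mean drinks/day in the past 30 days, as measured by both the TLFB and the Quantity/Frequency Questionnaire".

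**Collection.** Section 3 states: "During the baseline and the 3-month follow-up assessments, participants were given a Timeline Follow-Back Interview to assess past month alcohol use". Its account of the 3-month session says: "They completed all 1-month follow-up measures, as well as a computerized TLFB interview assessing past-month drinking". Section 5.3 describes a 1-month survey "which assessed mean drinks per day in the past 30 days, past month alcohol consequences, and motivation to reduce alcohol use", without TLFB. Q/F is the only other past-month alcohol-use measure listed.

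**Model.** Section 8.1 specifies "A single 2X2X2X2X2 ANCOVA", or an ordinal or binary counterpart if the distribution calls for it. Hypothesis 1 expects main effects "for the two factors consistent with Common Factors Theory (empathy and positive regard"), Hypothesis 2 adds voice and narrator, and Hypothesis 3 adds motivational content. Five factors are named.

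**Design.** Table 2 and the Research Design text in Section 4.1 give four two-level factors and 16 conditions. The Innovation text in Section 1.1 counts one factor "which is consistent with Common Factors Theory, and two of which are consistent with Media Equation Theory". Section 3 operationalizes the common-factors manipulation as empathic reflection and positive regard together.

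**The concern.** There are two faults.

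First, the model and Hypothesis 1 call for an effect that the randomization does not isolate. No condition has empathy without positive regard, or the reverse.

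Second, both instruments and both visits are called primary, but they do not cross. What remains is Q/F at 1 month, Q/F at 3 months and TLFB at 3 months. The plan names no lead, does not combine them, and does not say what follows if they differ. Two analysts could read the same data as supporting or failing a hypothesis, depending on the instrument or visit they quote. The end of Section 8.1 makes the choice among optimizing, refining and trying new factors depend on effectiveness and significance, without saying on which variable.

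**Working it through.** **1. The plan's own power figure.** Inputs from Section 8.1 are N=352 and d=0.3; alpha is 5% (Section 1.3.1). Two-sided testing is assumed because the plan does not state it. Each factor level has 352/2 = 176 participants. The noncentrality is 0.3/√(2/176) = 0.3·√352/2 = 2.81. Power is Φ(2.81 − 1.96) = 80.4%, or 80.1% by noncentral t, against 80% stated. The figure reproduces; a one-sided test would give 87.9%.

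**2. Five factors on a four-factor design.** A full five-factor effect-coded model has 2⁵ = 32 terms. If the fifth factor is positive regard, its column equals the empathy column in all 16 conditions, so only 16 of the 32 possible cells are occupied and the design matrix has rank 16. Half of the terms duplicate others, including the positive-regard main effect.

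**3. If the fifth factor is visit.** No section says so. A 1-month versus 3-month factor would fit Q/F. It would not fit TLFB, which has no 1-month value, and Hypothesis 1 would still name a factor that was not separately manipulated.

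**4. Consequence of having no lead variable.** The documents give no correlation between the variables, so ρ = 0.5 to 0.9 is assumed, common to all pairs. Other assumptions are normal data, complete follow-up, two-sided 5% tests and, under the alternative, d=0.3 on every variable. Each variable gives a test statistic with variance 1 and mean 0 (no effect) or 2.81 (d=0.3).

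- Three tests: the three variables are tested separately.
- Two tests: Q/F averaged over visits is one test, with noncentrality 2.81/√((1+ρ)/2), and TLFB at 3 months is the other. The two statistics correlate ρ·√(2/(1+ρ)), that is 0.58 at ρ=0.5 and 0.92 at ρ=0.9.

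Results by simulation:

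| Quantity, per effect | ρ=0.5 | ρ=0.9 |
|---|---|---|
| Three tests: results on different sides of 0.05, d=0.3 | 33% | 15% |
| Two tests: same | 18% | 9% |
| Three tests: at least one false positive, no effect | 12.5% | 8.4% |
| Two tests: same | 8.8% | 6.8% |
| Three tests: power if any one suffices | 95% | 87% |
| Three tests: power if all must agree | 62% | 73% |

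**5. Power of the averaged Q/F test.** If d=0.3 at both visits, the noncentrality is 2.81/√0.75 = 3.25 at ρ=0.5 (power 90%) and 2.81/√0.95 = 2.89 at ρ=0.9 (82%). If the effect halves by 3 months, the mean over visits is 0.75 of the full effect. The noncentralities become 2.44 and 2.17, and power is 68% and 58%. In that case 1 month alone has 80% power and 3 months alone has 29%.

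**The case against.** - **The model is recoverable.** A reader might infer that the primary analysis cannot be run at all. The documents do not support that: Sections 1.1, 3 and 4.1 fix four factors, so a 2X2X2X2 model can be reconstructed. What cannot be recovered is Hypothesis 1's separate positive-regard effect.
- **The 33% depends on the reading.** Quoting 33% to 15% alone would take the least favourable reading. With visit as a repeated factor there are two tests, and the figures roughly halve. Both ranges are needed.
- **Different p-values are not always a conflict.** A single test misses a true d=0.3 in about 20% of trials, so part of the split is ordinary sampling error. An effect may also fade between visits. This stands. It explains why results split but does not say which one decides.
- **The decision rule is softer than a single threshold.** A reader might infer that one p<0.05 commits the team to an optimized intervention. Section 8.1 distinguishes clear effectiveness, some effectiveness and no significant effects, and every branch is further development work.
- **The study is exploratory.** The design considerations after Section 8.1 say so. Strict familywise control is therefore not required, but exploratory status does not supply the missing rule or separate two combined components.
- **Q/F need not lead.** The Measures text in Section 3 credits TLFB with high reliability and makes no such claim for Q/F. Choosing Q/F is defensible, not compulsory.

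**Conclusion.** Wrong as written, on two counts. The five-factor model and Hypothesis 1 do not match a four-factor design in which empathy and positive regard form one factor, and the primary outcome pairs both instruments with both visits although TLFB has no 1-month value and nothing leads. Both follow from the text and need no assumption.

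The size of the second fault does rest on assumptions: correlation 0.5 to 0.9, the same true d on every variable, normal data and complete follow-up. The plan allows ordinal or binary models and gives no dropout rate, so the percentages are indicative. Across both readings, primary results split around p=0.05 in about 9% to 33% of trials with a true d=0.3. The false-positive rate per effect, if any one result is accepted, is about 7% to 12.5%. Each single test still keeps its own 5%; the excess arises only when the reported result can be picked from several. The documents do not support the stronger inference that the trial is invalid or that its factorial main effects cannot be tested.

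**What to change.** 1. **Model and hypotheses.** Correct the model to 2X2X2X2, with visit as a repeated factor if that was intended. Restate Hypothesis 1, and the common-factor wording in Hypotheses 4 and 5, for the single combined empathy/positive-regard factor.
2. **Lead variable.** Name one. Q/F averaged over 1 and 3 months and adjusted for baseline Q/F, in a repeated-measures model of the type the distribution requires, is the only option that meets the present two-visit definition. TLFB at 3 months is a defensible alternative if the definition is changed to 3 months. Report the others as supportive.
3. **Decision rule.** Tie the rule at the end of Section 8.1 to that variable and to a listed set of effects, and state the chance of at least one false positive when nothing works. Treating the effects as independent, this is 1 − 0.95^k: 54% for all 15 effects, 40% for the 10 main and two-way effects, and 19% for the four main effects. Naming one variable does not lower these; only a shorter list does. An exploratory study may accept any of them if declared.

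**Cost.** This is a wording change if made before outcomes are seen by condition. One instrument becomes supportive. Averaging gains power if the effect lasts (90% to 82%) and loses it if the effect halves by 3 months (68% to 58%, against 80% at 1 month alone). Section 7 describes the analysis in the past tense, so it may be too late to prespecify. If results by condition are known, label the choice post hoc and report all three variables side by side.
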